ACT intervention. The overriding goals of the ACT intervention are to (1) develop *acceptance*-related skills for dealing with internal smoking cues while (2) enhancing an enduring commitment to quit smoking [3]. Participants are encouraged to make behavioral choices on the basis of commitment to goals linked to life values, and not on the basis of seeking to modify or alleviate certain sensations, emotions, and thoughts. To achieve these goals, the intervention will focus on ACT's core interdependent processes: *acceptance* and *commitment*. In ACT for smoking cessation, *acceptance* refers to allowing one's self to have, without defense, the sensations, emotions, and thoughts that cue smoking [3-4, 5-6]. The process of *commitment* in ACT means committing to taking actions to quit smoking even in the presence of sensations, emotions, and thoughts that cue smoking.

Comparison app. To address the question of whether Quit2Heal is more efficacious than an app following USCPG, we chose QuitGuide as the ideal comparison intervention for four key reasons. First, it is one of the few apps (of the 400 available) that follow the USCPG [7]. Second, its content and structure are directly based on Smokefree.gov, the most accessed cessation website in the world. Third, QuitGuide's content is non-proprietary and free to the public, thereby providing maximal transparency, accessibility, and replicability. Finally, because of our pilot RCT and iCanQuit RCT, QuitGuide is now the only app following USCPG with adult quit rate estimates that are based on a clinical trial [8].

Recruitment. Our goal is to have 600 participants screen eligible to randomize 60 study participants. To recruit nationally, we will work with Fred Hutch Communications and Marketing to develop a study media kit that includes a recruitment website, press

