Enrollment. We will use the identical enrollment method proven successful in our iCanQuit ACT smartphone RCT. Specifically, for participants who screen eligible on the recruitment website and provide their email address, we will instantly send them an email (and two reminders over a 14-day period) inviting them to complete a secured online survey to provide informed consent and complete the baseline assessment. Those not consenting and completing the online enrollment process within 14 days will be sent an email notifying them that they were not enrolled and provide both the smokefree.gov website and the [name] phone number to reach their state's quitline. Those randomized will be emailed a secured link to download their app (either Quit2Heal or QuitGuide). All participants will be emailed identical once weekly reminders to use their assigned intervention.

Two-month post randomization follow-up survey. At baseline, we will collect email, phone, and mailing address information as well as optional contact information on at least 2 collateral contacts. At 2 months post randomization, participants will be sent an email with an invitation to complete the 2-month follow-up survey. An additional two reminders will be sent within 9 days. A phone survey will be conducted for those not responding by the 12th day. There will be 12 attempts made over 12 days. Lastly, a reminder letter will be sent that will include a \$2 bill pre-incentive to encourage participation. We will send reminder letters at each follow-up for those non-responders using an "Address Service Requested" envelope, for automatic forwarding to new mailing addresses. Each survey and Internet tracking will also collect address information. A final postcard with just two questions will be mailed out if follow-up rates are below 70%. All respondents will be mailed \$25 after completing the survey, with a \$10 bonus if they complete the survey online within 24 hours.

MEASURES AND STATISTICAL ANALYSIS PLAN

Table 2. Participant surveys and time points when they will be administered. (All participants)

Measure	Screening	Baseline	2-month	Purpose
Eligibility & Enrollment (24 items)	х			Eligibility, Enrollment, & Stratification
Demographics (24 items)		Х		Stratification & Exploratory
Nicotine Dependence (6 items)		Х	Х	Stratification & Aim 1
Smoking/Tobacco History (2 items)		x		Aim 1, Aim 4, and Exploratory
Tobacco Use (9 items)		Х	х	Aim 4
Alcohol Use (4 items)		Х	Х	Aim 4

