PTSD Symptoms (6 items)		x	Х	Aim 4
Post Traumatic Growth Inventory (21 items)		х	x	Aim 4
Generalized Anxiety Symptoms (7 items)		x	x	Aim 4
Social Anxiety Symptoms (3 items)		x	х	Aim 4
Depression Symptoms (10 items)		x	x	Aim 4
Distress Tolerance (6 items)		Х	Х	Aim 4
Values (10 items)		x	Х	Aim 4
Internalized Shame Symptoms (5 items)		х	x	Aim 4
Self-Compassion (10 items)		x	x	Aim 4
Smoking and Cancer Outcome Expectancies (4 items)		x	x	Aim 4
Quitting Self-Efficacy (1 item)		x		Aim 4 and Exploratory
Internalized and Perceived Stigma Items (9 items)		x	Х	Aim 4
Mobile Device Use (6 items)		х		Eligibility and Aim 1
Receptivity/utilization (14 items)			Х	Aim 2 and Aim 3
Cessation & Extra Aids (5 items)			Х	Aim 1, Aim 3, and Exploratory
Willingness to discuss (1 item)			X	Follow-up
Acceptance of cues (18 items)		Х	Х	Aim 4 & Exploratory

Analyses. Our aims examining feasibility, engagement, usability, and cessation are all exploratory. Analyses based on follow-up survey items will be limited to participants who complete the 2-month follow-up survey. All other analyses will include all randomized participants.

Feasibility of recruitment methods. We will assess the number and proportion of study participants recruited directly by the cancer treatment center and through Facebook ads. A table with N (%) by treatment arm will be provided.

Engagement and receptivity to the Quit2Heal app. We will assess the number of times participants log into their assigned apps and total time spent on the apps based on data automatically logged on the secure server. Receptivity to the apps will be assessed by two items on the 2-month follow-up survey. One asks participants to rate the overall usefulness of their assigned Quit2Heal app for quitting smoking. Ratings will be dichotomized as "somewhat", "mostly", or "very" useful vs. lower ratings. The second item allows participants to provide comments or suggestions that will allow us to qualitatively assess receptivity to the app and aid in future development of the app. Tables with N (%) or Mean (SD) by treatment arm will be provided.

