Usability of the Quit2Heal app. We will compare the two arms on items measuring the usability of the assigned program using descriptives. If participants indicate that they are willing to discuss their experience in the study, we will contact them to inquire about their user experience with the app. Responses will be used to qualitatively assess ease of use, appeal of the app design, and suggestions users may have for improvements.

Cessation outcomes and cessation progress at 2-month follow-up. We will report the 30-day point prevalence quit rate at 2-months post randomization, as well as secondary cessation outcomes 7-day and 24-hour point prevalence abstinence. We will provide both complete case and missing=smoking results for each study arm. Quit2Heal vs. NCI Quit Guide cessation rates will be compared using logistic regression, adjusting for the three factors used in stratified randomization: Heaviness of Smoking Index, Commitment to Quitting Smoking Score, and recruitment method.

Cessation progress outcomes will include number of 24-hour quit attempts, change in number of cigarettes smoked per day since randomization, nicotine dependence level, acceptance of cravings to smoke, commitment to quitting, and use of nicotine replacement therapy or medications to aid quitting. Tables with N (%) or mean (SD) by treatment arm and p-values obtained from logistic regression, linear regression, or negative binomial regression models adjusted for randomization factors will be provided.

PROTECTION OF HUMAN SUBJECTS

Risks to the Subjects

Human subjects' involvement and characteristics. We will conduct a two-arm randomized controlled trial that compares the Quit2Heal cancer-patient specialized application-based ACT to an application-based smoking cessation intervention following US Clinical Practice Guidelines (Smokefree.gov). To balance baseline variables

between the two conditions, following enrollment we will randomize with stratification according to these known predictors of smoking cessation: nicotine dependence (Heaviness Smoking Index cut off score of 4 [9]), motivation to quit (Commitment to Quitting Scale cutoff score of 4 [10], and recruitment method (clinic vs. social media). The hypothesized moderators will be measured at baseline. The hypothesized mediators will be assessed at both baseline and two months post randomization, while cessation and progress outcomes will be measured at 2 months post randomization.

Potential Risks

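### Acceptance of cravings, and secondarily change in cigarettes per day, is compared between arms without adjusting for the measure's own baseline, which loses precision at moderate or high baseline to 2-month correlations

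*Combined protocol and SAP*

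**What the plan says.** The section Cessation outcomes and cessation progress at 2-month follow-up describes the cessation models as "adjusting for the three factors used in stratified randomization: Heaviness of Smoking Index, Commitment to Quitting Smoking Score, and recruitment method". The progress outcomes include "change in number of cigarettes smoked per day since randomization, nicotine dependence level, acceptance of cravings to smoke", commitment to quitting, quit attempts and use of medication. For all of these, "p-values obtained from logistic regression, linear regression, or negative binomial regression models adjusted for randomization factors will be provided". No section adds an outcome's own baseline, and none says which of the three models each outcome gets.

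Table 2 marks the rows that begin "Acceptance of cues (18 items" and "Tobacco Use (9 items" for both baseline and 2 months. The ACT intervention section says that the app aims to build acceptance-related "skills for dealing with internal smoking cues while (2) enhancing an enduring commitment to quit smoking". The Analyses paragraph states: "Our aims examining feasibility, engagement, usability, and cessation are all exploratory".

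**The concern.** Acceptance is one of the two processes the app is built to change, and its baseline goes unused when the arms are compared on it. It is not a stratification factor either, so in a trial of 60 a chance imbalance at baseline would pass straight into the arm difference. Baseline cigarettes per day is used through the change score, which fixes its slope at 1 instead of estimating it, and partly through HSI. What is at stake is the width of the confidence interval, and so the p-value, in a small pilot where adjusting would need no new data.

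**Working it through.** The plan gives no power, SD, precision target or baseline to 2-month correlation, so there is no figure of its own to reproduce.

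**Inputs from the documents**
- 60 randomized (Recruitment). Survey outcomes are analysed in 2-month completers only (Analyses).
- n = 42 is 70% of 60. The 70% is the trigger for the final postcard (Two-month post randomization follow-up survey). It serves here as a scenario and is not a retention forecast.
- Three covariates besides arm.

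**Assumptions**
- 1:1 allocation, linear model, equal variance at baseline and 2 months.
- Correlation ρ between baseline and 2 months of 0.3, 0.5 or 0.7.

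**Variance of the arm difference.** With residual variance s² and q covariates beyond arm, the expected variance is s² × (4/n) × (n−3)/(n−3−q).
- Planned, q = 3: (4/42) × (39/36) = 0.1032 s².
- With own baseline, q = 4: (4/42) × (39/35) = 0.1061 s².
- The ratio of multipliers is 36/35 = 1.029, or 54/53 = 1.019 at n = 60. This is the whole price of the term: 2.9% at n = 42 and 1.9% at n = 60 if ρ = 0 (2.7% and 1.8% by simulation).

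**Acceptance.** If baseline acceptance is unrelated to the covariates already in the model, the variance ratio is (1−ρ²) × 36/35. If it correlates 0.5 with a Commitment score in the model, and Commitment acts only through it, the ratio is (1−ρ²)/(1−0.25ρ²) × 36/35. Participant equivalents are 42/(1−cut) − 42, using the simulated cut (40,000 replicates per cell).

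| ρ | Unrelated: formula | Simulated cut | Participants | r = 0.5: formula | Simulated cut | Participants |
|---|---|---|---|---|---|---|
| 0.3 | 1 − 0.91×1.029 = 6.4% | 6.5% | 2.9 | 1 − 0.931×1.029 = 4.2% | 4.0% | 1.8 |
| 0.5 | 1 − 0.75×1.029 = 22.9% | 22.6% | 12.3 | 1 − 0.800×1.029 = 17.7% | 17.7% | 9.0 |
| 0.7 | 1 − 0.51×1.029 = 47.5% | 47.9% | 38.6 | 1 − 0.581×1.029 = 40.2% | 40.1% | 28.1 |

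In the unrelated case the break-even is ρ = √(1/36) = 0.17 at n = 42 and √(1/54) = 0.14 at n = 60. In that case the 95% interval half-width goes from 0.651 SD to 0.630/0.572/0.472 SD. The difference detectable with 80% power goes from 0.92 SD to 0.89/0.81/0.67 SD.

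**Change in cigarettes per day.** A change can be negative, so of the listed models only linear regression takes it as it stands. Let v be the share of baseline variance that HSI leaves unexplained. The variance ratio is (1+ρ)/[(1−ρ)v + (1+ρ)] × 36/35. With an assumed HSI to baseline correlation of 0.8:
- HSI as a score, v = 1 − 0.64 = 0.36: cuts of 13.8/8.2/3.3% (simulated 13.7/8.3/2.6%, or 6.7/3.8/1.1 participants).
- HSI split at the median, v = 1 − (2/π) × 0.64 = 0.593: cuts of 22.0/14.1/6.9% (simulated 21.3/14.3/7.2%, or 11.4/7.0/3.3 participants).
- Score reading, break-even: 0.36(1−ρ)/(1+ρ) = 1/35 gives ρ = 0.85.
- Moving the 0.8 from 0.6 to 0.9 moves the simulated cuts from 27.1/17.8/9.5% to 17.7/11.0/5.5% (split) and from 24.2/14.7/7.9% to 7.0/3.2/0.9% (score).

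**Skipped baseline items.** Suppose 2 of 42 lack a usable baseline acceptance score and are dropped. The multiplier becomes (4/40) × (37/33) = 0.1121, against 0.1032 planned, a ratio of 1.087. At ρ = 0.3 the ratio is 0.91 × 1.087 = 0.989, a gain of about 1% (unrelated case), or 0.931 × 1.087 = 1.012, a loss of about 1% (r = 0.5). At ρ = 0.5 the gains are still about 18% and 13%.

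**Commitment outcome.** Entering its baseline as a score instead of a median split cuts variance by 1 − (1−ρ²)/(1−(2/π)ρ²) = 3.5/10.8/25.9%, with no degree of freedom lost. The cutoff of 4 need not be the median.

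**The case against.** The strongest reply is that this is a preference for efficiency and not an error. The comparisons are exploratory, adjusting for the stratification factors is coherent, and the plan misses no precision target because it sets none. That stands, and it limits the weight of the point. The plan does commit to p-values for these outcomes, however, and a covariate is best fixed before the data are seen.

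Every gain also rests on an assumed correlation. At 0.3 the acceptance interval narrows by only about 3% (0.651 to 0.630 SD), which few readers would notice. That stands too.

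The cigarettes-per-day part is weaker. The outcome is already a change, and the title of the HSI reference shows that the index is built partly on cigarettes per day. The adjustment sentence names the index and the score, while the cutoffs appear only where stratification is described ("nicotine dependence (Heaviness Smoking Index cut off score of 4"). On the score reading little is left to gain.

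Three stronger readings are tempting, and the documents do not support them.
- A reader might infer bias. Under randomization the planned comparison is valid without the baseline.
- A reader might infer that every progress outcome ignores its baseline. Commitment and nicotine dependence are at least partly represented by the stratification factors, and the plan itself labels HSI as nicotine dependence.
- A reader might take 3/12/39 participants as the size of the loss. That is the favourable case. The ACT intervention section treats acceptance and commitment as depending on each other, and the Commitment score is already in the model, so 2/9/28 belongs beside it.

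**Conclusion.** The point holds as a minor loss of precision in exploratory outcomes, mainly for acceptance of cravings. It is worthwhile at a correlation of about 0.5 or more, small at 0.3, and slightly negative below about 0.17 at n = 42. For cigarettes per day the gain is modest and depends on how HSI is coded. No decision rule in the plan turns on either comparison.

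The figures rest on correlations that the documents do not give, on linear models, and on 42 analysed. Two identifications are inferred: that the Table 2 acceptance-of-cues scale is the acceptance-of-cravings outcome, and that the tobacco-use items hold baseline cigarettes per day.

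**What to change.** In the linear models for acceptance of cravings and for cigarettes per day, add the continuous baseline value of the same measure to the randomization factors. Keep participants with an incomplete baseline score in the model, for example by prorating the scale or by single mean imputation of the baseline covariate. The section Protection against emotional upset or embarrassment lets participants skip items, and the acceptance scale has 18.

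For the commitment outcome, enter the baseline Commitment score as a score and not as the cutoff split.

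The cost is a few SAP sentences, one degree of freedom in each model that gains a term, and a simple imputation step. No new data are needed.

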Randomized trial experimental design. We will conduct a two-arm randomized controlled trial that compares application-based ACT to an application-based smoking cessation intervention following US Clinical Practice Guidelines (Smokefree.gov). To balance baseline variables between the two conditions, following enrollment we will randomize participants.

Figure 1. Experimental Design

APPROACH

We will conduct a randomized effectiveness trial comparing our ACT smoking cessation application Quit2Heal to the NCI's Quit Guide application. Specifics on our pilot trial, research team, and research strategy are the following:

Eligibility Criteria: (1) age 18 or older, (2) diagnosed with cancer in the past 12 months, or currently receiving or planning in the next 3 months to receive cancer treatment, (3) has smoked a cigarette (even a puff) in the past 30 days, (4) interested in learning skills to quit smoking, (5) willing to be randomly assigned to either smartphone application, (6) resides in US, (7) has at least daily access to their own smartphone, (8) knows how to login and download a smartphone application from the Apple app store or Android Play app store, (9) willing and able to read in English, (10) not currently using cessation medications or enrolled in other smoking cessation programs, and (11) has never used the NCI's Quit Guide smartphone application. To increase follow-up retention, eligiblity criteria also include: (12) willing to complete one follow-up survey, (13) provide email, phone, and mailing address. Participants not eligible for or interested in randomization will be given the given the smokefree.gov website, the [name] phone number to reach their state's quitline, and the NCI's Quit Guide smartphone application.

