treatment groups will be given information on pharmacotherapy for smoking cessation (e.g., nicotine patch) and how to obtain these medications.

Reporting Breaches and Complaints. Taken together, these measures will minimize risks to study participants. However, should a breach/complaint occur, or if a participant is not pleased with any of the surveys, or with the study's procedures, the study's scientific staff will attempt to address the concerns; if unsuccessful, the breach/complaint will be reported to the IRB office, and the participant will be referred to [name], Fred Hutch IRO Director.

Potential Benefits of the Proposed Research to the Subjects and Others.

Successfully assisting cancer patients who smoke to quit would have significant positive benefits to their health. Overall, participants assigned to either of the two interventions have the potential to benefit by quitting smoking and the potential short- and long-term health benefits of quitting on their cancer treatment and prognosis, and overall lifetime health.

Importance of Knowledge to Be Gained. The proposed intervention shows exciting promise for improving cessation rates among cancer patients, who currently do not have standard cessation interventions as part of their treatment. If effective, the public health impact of this low-cost intervention is significant. Even if the intervention is not better than our standard care control, it suggests the new intervention should be disseminated as a reasonable alternative to other publicly available application-based interventions.

INCLUSION OF WOMEN AND MINORITIES

The population for this study will be 60 adult male and female cancer patients who currently smoke and want to quit, or have quit smoking within in the past 30 days. Recruitment and eligibility screening methods are designed to achieve a broad representation of adult smokers that is 50% female and 25% minority race/ethnicity. The expected gender and race/ethnic distribution of the trial participants is reported in the Targeted/Planned Enrollment Table.

TARGETED/PLANNED ENROLLMENT TABLE

Total Planned Enrollment:

60

TARGETED/PLANNED ENROLLMENT: Number of Subjects					
Ethnic Category	Sex/Gender ¹				
	Females	Males	Total		
Hispanic or Latino	2	2	4		
Not Hispanic or Latino	43	13	56		
Ethnic Category: Total of All Subjects *	45	15	60		

Racial Categories			
American Indian/Alaska Native	1	0	1
Asian	0	1	1
Native Hawaiian or Other Pacific Islander	0	0	0

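### A result showing Quit2Heal is not better than QuitGuide is read as support for dissemination, which a 60-person exploratory superiority comparison cannot give

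*Combined protocol and SAP*

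**What the plan says.** The human-subjects part of the combined protocol and SAP, under Importance of Knowledge to Be Gained, states: "Even if the intervention is not better than our standard care control, it suggests the new intervention should be disseminated as a reasonable alternative". The sentence goes on to name other publicly available apps as what Quit2Heal would be an alternative to.

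The rest of the document describes a different kind of trial:

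- Comparison app gives the question as one of superiority: "To address the question of whether Quit2Heal is more efficacious than an app following USCPG".
- Recruitment gives the size: "Our goal is to have 600 participants screen eligible to randomize 60 study participants".
- Analyses gives the status: "Our aims examining feasibility, engagement, usability, and cessation are all exploratory".
- Cessation outcomes and cessation progress at 2-month follow-up gives the method: "Quit2Heal vs. NCI Quit Guide cessation rates will be compared using logistic regression, adjusting for the three factors used in stratified randomization". Quit rates are to be shown by arm, both for complete cases and with missing counted as smoking.

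The document states no non-inferiority or equivalence hypothesis, no margin, no confidence interval for the difference in quit rates, no significance level and no power calculation.

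**The concern.** Calling the new app a reasonable alternative that should be disseminated is in substance a non-inferiority conclusion. It needs evidence that Quit2Heal is not worse than QuitGuide by more than some tolerable amount. Failing to show that it is better is not that evidence: in a small trial, this outcome is likely whether the new app is better, equal or worse.

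The document's own Significance section lists what continued smoking does to cancer patients, including treatment complications, recurrence and survival. Spreading a materially less effective cessation app in this population would therefore matter. The sentence also reaches beyond the comparison made, since QuitGuide is the only comparator but the conclusion extends to other public apps.

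The point is limited to a non-significant difference. The document does not discuss a significantly worse result, although taken literally its wording would cover one.

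**Working it through.** **Inputs from the document.** 60 randomized in two arms; binary 30-day quit outcome at 2 months; complete-case and missing=smoking results. The 60 cannot be reproduced, because no quit rate, effect size, significance level or power is given. The 70% follow-up figure is only the trigger for a final postcard.

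**Assumptions.** 1:1 allocation (30 per arm), two-sided 5%, true quit rates between 5% and 20%. For a complete-case illustration, 70% follow-up, so 0.70 × 30 = 21 per arm.

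**1. What a tie leaves open.** The Newcombe 95% interval combines the Wilson limits (l, u) of the two arms. With the same x/n in each arm, the half-width is √[(p − l)² + (u − p)²].

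- 3/30 each: Wilson limits 0.0346 and 0.2562, so √(0.0654² + 0.1562²) = 0.169.
- 6/30 each: limits 0.0951 and 0.3731, so √(0.1049² + 0.1731²) = 0.202.
- 4/30 and 5/30 each: 0.182 and 0.193.
- 2/21, 3/21 and 4/21 each: 0.206, 0.224 and 0.238.

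An exact tie is thus compatible with a deficit of about 17 to 20 points at 30 per arm, and about 21 to 24 points at 21 per arm.

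**2. How often a worse app gives a non-significant result.** Sum the product of the two binomial probabilities over all pairs of quitter counts that give p > 0.05.

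| True rates, Quit2Heal vs QuitGuide | n per arm | Test | Significantly worse | No significant difference |
|---|---|---|---|---|
| 10% vs 20% | 30 | Chi-square | 19.3% | 80.6% |
| 10% vs 20% | 30 | Fisher | 9.5% | 90.4% |
| 5% vs 10% | 30 | Chi-square | 10.3% | 89.4% |
| 5% vs 10% | 30 | Fisher | 1.9% | 98.1% |

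At 21 per arm and 10% vs 20%, significantly worse falls to 14.3% (chi-square) and 7.8% (Fisher).

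The planned analysis is an adjusted logistic model. Simulating it (4,000 trials per scenario, assumed factor prevalences and odds ratios) for 10% vs 20% gave significantly worse in 11–13% of trials with a Wald test and 22–24% with a likelihood-ratio test. The plan does not say which test applies. Either way, roughly three quarters or more of such trials would not flag the halving.

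**3. What the claimed conclusion would need.** If both apps truly had 20% quit rates, the chance that the lower Newcombe limit lies above −10 points (a halving ruled out) is 14.9% at 30 per arm. At 10% each, the chance of ruling out a 5-point deficit is 6.9%. The numbers for 80% power, one-sided 2.5%, follow from

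n per arm = (1.960 + 0.842)² × 2p(1 − p) / margin², with (1.960 + 0.842)² ≈ 7.849.

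- p = 0.20, margin 0.10: 7.849 × 0.32 / 0.01 = 251.2, so 252 per arm (504 in total).
- p = 0.10, margin 0.05: 7.849 × 0.18 / 0.0025 = 565.1, so 566 per arm (1,132 in total).

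These margins only illustrate scale; the document sets none.

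**The case against.** The strongest reply is that the sentence is rationale text. It defines no hypothesis, threshold or decision rule, no planned analysis depends on it, and it is hedged as a suggestion. The SAP calls the aims exploratory and the study is described as a pilot, so a careful reader would not take the cessation result as confirmatory. All of this is true, and it limits the weight of the point. It does not repair the sentence: what is suggested is that the app should be disseminated, and nothing in the analysis sections offers another reading of a null result. The exploratory label argues against the conclusion without withdrawing it.

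A second reply is that the document says not better, which need not mean p > 0.05. In the 10% vs 20% scenario, Quit2Heal would have the lower observed quit rate in about 82% of trials, visible in the by-arm results, and the document does not say such a result would be called a reasonable alternative. This is fair. The 81–90% figure depends on reading not better as non-significant, which is natural given the planned p-values but is not stated. The interval widths do not depend on that reading.

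Third, the simulation rests on several assumed inputs. That also stands; the conclusion does not need it.

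**Conclusion.** The concern holds. The stated inference is wrong as written: this design cannot turn a failure to show superiority into support for dissemination. With 30 per arm, even identical observed quit rates of 10% to 20% leave a deficit of about 17 to 20 points open. A true halving from 20% to 10% would go undetected in about 81–90% of trials by the unadjusted tests. The exact figures rest on assumed allocation, significance level and quit rates. The conclusion does not: no observed rate from 10% to 30% gives a tied interval narrower than about ±17 points at 30 per arm. The fault affects interpretation only; no estimate, test or participant is touched. It should be fixed before results are written up.

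**What to change.** Under Importance of Knowledge to Be Gained, replace the sentence with:

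> A non-significant difference in this pilot is inconclusive; it will not be read as equivalence or as support for dissemination, and will inform only whether and how to design a powered trial.

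Under Cessation outcomes and cessation progress at 2-month follow-up, add:

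> The Quit2Heal minus QuitGuide difference in quit rates will be reported with its 95% CI (unadjusted, Newcombe method), for both the complete-case and the missing=smoking results.

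The interval method should be named, because with perhaps 3 to 6 quitters per arm the choice affects the limits and the planned logistic model yields an odds ratio. An adjusted difference would also be acceptable if its method is specified.

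The cost is one sentence replaced and one added. Data collection, endpoints, model and sample size do not change. The stated promise of the pilot becomes slightly less favourable.
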